#### 6.6 Other Safety Considerations

Any significant worsening or new findings noted during post-intervention follow-up visit or any other potential safety assessments performed during the study, whether or not they are required by the protocol, should be recorded on the appropriate AE form.

#### 6.6.1 Follow-up of Adverse Events

During and following a subject's participation in a clinical study, the Investigator should ensure that adequate medical care is provided to the subject for any AEs, including clinically significant laboratory values related to the study. The Investigator should inform the subject when medical care is needed for AEs.

The period for reporting new AEs will continue until the post-intervention follow-up visit (final study visit).

All non-serious AEs classified as possibly/probably related to the investigational product must be followed until the subject has recovered and all queries have been resolved. However, cases of chronic conditions can be closed if determined by clinician as stable, with an outcome of "recovering" or "not recovered." If a subject died from another event, these cases can be closed with an outcome of "not recovered."

All other non-serious AEs must be followed until the outcome of the event is "recovering" (for chronic conditions), or until the end of the post-intervention follow-up stated in the protocol, whichever comes first, and until all queries related to these AEs have been resolved. If a subject died from another event, these cases can be closed with an outcome of "not recovered."

The Investigator must enter follow-up information about non-serious AEs on the AE form within the CRF.

Queries or follow-up requests from ICON GPHS should be responded to within 14 calendar days, unless otherwise specified. The Investigator must forward follow-up information on SAEs to the requestor within 5 calendar days of obtaining the request for follow-up information.

All SAEs must be followed until the outcome of the event is recovered, recovered with sequelae, or fatal and until all queries have been resolved. For cases of chronic conditions and cancer or if the subject dies from another event, follow-up until the outcome categories are "recovered," "recovered with sequelae," or "fatal" is not required, as these cases can be closed with an outcome of "recovering" or "not recovered."

#### 6.6.2 Pregnancy

While women of childbearing potential are eligible for the study, they must agree to use an approved form of birth control (see Section 3.1 Inclusion Criteria) over the duration of the study period. Women of childbearing potential are defined as any female who has experienced menarche and who is NOT permanently sterile or postmenopausal. Postmenopausal is defined as 12 consecutive months with no menses without an alternative medical cause. If there is any

question that a subject will not be reliable in the adherence to this requirement, they should not be entered into the study.

Study subjects must be instructed to notify the study site Investigator immediately if they suspect pregnancy during the course of the study and for a period of 4 weeks following study discharge. Subjects who become pregnant will be instructed to immediately discontinue study product. The Investigator must report any pregnancy during the study to the Medical Monitor within 14 calendar days of obtaining the information using the Pregnancy Form and the Pregnancy Follow-up Form, respectively. Pregnancy complications must be recorded as AEs or SAEs if meets criteria. If the infant has a congenital anomaly or birth defect, the anomaly or defect must be reported and followed as an SAE.

### 7 Clinical Monitoring/Site Monitoring Plan

Monitoring will be conducted to ensure that human subject rights and well-being are protected, data are accurate, complete, and verifiable from source documents, and the study complies with the protocol/amendment(s), and applicable regulatory requirements.

In order to ensure protocol compliance, monitoring visits will occur at scheduled intervals prior to, during, and at study completion. The visit frequency will be defined in a monitoring plan and communicated to the Investigators.

A separate study-specific monitoring plan will define the monitoring details such as the frequency of monitoring visits and percentage and selection of charts/source documentation to be monitored. An ICON GPHS CRA will be responsible for the clinical monitoring at the study sites. The CRA will operate independently from the study sites and will comply with ICON GPHS SOPs. The CRA will ensure that the Investigators understand the investigational status of the study product, all requirements of the protocol, and his/her regulatory responsibilities as an Investigator. The CRA will visit the clinical site in accordance with the monitoring plan to assess compliance with the protocol, verify accuracy and completeness of the data, perform accountability of study product, and review essential regulatory documents.

The investigational sites will provide direct access to all study-related documents and records maintained by the Investigators, including but not limited to study-related source data for the participants in this study.

The Investigators are ultimately responsible for ensuring that the CRA's findings are addressed.

#### **8** Statistical Considerations

This section outlines the basic statistical approach for the study. A final statistical analysis plan will be written and approved before the database lock. This plan will specify all statistical methods and plans for analysis.

### 8.1 Study Hypotheses

The hypothesis to be tested in this study is that AMPHORA will prevent the sexual transmission of CT. As noted above, CT infection in women is associated with higher vaginal pH (pH >4.5) (10). This finding is supported by other reports in the literature (7). In addition, a higher vaginal pH has been associated with increased transmission of GC (28). AMPHORA also contains a relatively high concentration of lactic acid (1.8% w/v). Lactobacilli inactivate CT through the production of lactic acid (29). Thus, AMPHORA should reinforce the ability of lactobacilli to maintain healthy levels as well as provide additional lactic acid that may act directly in preventing CT infection.

#### 8.2 Sample Size Considerations

The primary analysis is a comparison between proportion of subjects who experience at least one CT infection among the intervention groups (AMPHORA or placebo).

It is assumed that the proportion of subjects experiencing at least one infection of CT during the study period (incident infection of CT) up to Week 16 under placebo will be 22.5%. An incident infection of CT of 13% in the subjects receiving active treatment (ie, a treatment difference of 9.5%) is considered clinically relevant for AMPHORA versus placebo. Using a Chi-square test for the primary endpoint, 253 analyzable subjects per treatment group (506 subjects total in the ITT population) will yield approximately 80% power to detect 9.5% treatment difference with a 2-sided 5% type I error rate (SAS 9.3 PROC POWER). Assuming that 20% of the total enrolled subjects will be lost to follow-up, 15% will be re-infected with GC (making them ineligible for the primary endpoint analysis), and 5% will be deemed ineligible for analysis due to antibiotic use, the total sample size planned for this study is 844 subjects.

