#### 3.1 Inclusion Criteria

- 1. Healthy female subjects between 18 and 45 years of age, inclusive
- 2. Ability to understand the consent process and procedures
- 3. Subjects agree to be available for all study visits
- 4. Written informed consent in accordance with institutional guidelines
- 5. Negative pregnancy test
- 6. Negative CT and GC NAAT at screening or positive CT or GC NAAT and receives SOC treatment prior to enrollment
- 7. Agree to use a woman-controlled method of contraception that is not directly delivered to the vaginal mucosa (with the exception of a vaginal ring) throughout the duration of the study, such as oral contraceptives, birth control implants, intrauterine

- devices (IUDs), or tubal ligation. Condom use only is not an acceptable form of contraception for this study
- 8. Able and willing to comply with all study procedures
- 9. Documented (as part of a retrievable medical record) CT or GC infection within 16 weeks prior to enrollment. Acceptable documentation will include:
  - Lab reports confirming CT/GC infection OR
  - Third party clinic note confirming previous CT/GC infection and indicating the date of diagnosis and/or date of treatment
- 10. Reports vaginal sexual intercourse with a male partner at least three times per month in the previous month and anticipates vaginal sexual intercourse regularly for the duration of the study
- 11. Agree to abstain from douching or any form of vaginal suppository use (other than investigational product) during course of study

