#### 3.2 Exclusion Criteria

- 1. Participation in any study with an investigational compound or device within 30 days prior to signing informed consent
- 2. In the opinion of the Investigator, has a history of substance or alcohol abuse in the last 12 months
- 3. In the opinion of the Investigator, has issues, conditions, or concerns that may compromise the safety of the subject, impact the subject's compliance with the protocol requirements, or confound the reliability of the data acquired
- 4. Is an Evofem, ICON GPHS, or clinical site employee regardless of direct involvement in research activities, or their close relative
- 5. Pregnant (or actively trying to become pregnant), or breastfeeding
- 6. Women who have undergone a total hysterectomy (had uterus and cervix removed)
- 7. Inability to provide informed consent
- 8. Has a history or expectation of noncompliance with medications or intervention protocol
- 9. Has engaged in sexual vaginal intercourse or douching, or used any form of vaginal suppository or intravaginal device (with the exception of contraceptive vaginal ring or tampons) for 24 hours prior to enrollment (may be enrolled at a later date if all other criteria are met)
- 10. Menstruating at enrollment (may be enrolled at a later date if all other criteria are met)
- 11. Is currently being treated, or have been treated, for a period of 21 days prior to enrollment, with specific antibiotics known to be used for the treatment of CT or GC:
  - Azithromycin

- Erythromycin
- Tetracycline
- Minocycline
- Doxycycline
- Levofloxacin
- Ofloxacin
- Ceftriaxone
- Cefixime
- 12. In the opinion of the Investigator, has signs/symptoms that indicate persistence of chlamydia or gonorrhea infection diagnosed at screening, new interval infection and/or a failure to comply with or complete the prescribed treatment regimen following a positive screening NAAT
- 13. Women who regularly use douches, vaginal medications, products, or suppositories
- 14. Women who are currently using contraceptive products that are directly delivered to the vaginal mucosa, such as diaphragms, spermicides, or any vaginally applied or inserted products containing N-9
- 15. Children, pregnant women, prisoners, and other vulnerable populations

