#### 5.5.4 Concomitant Medications

Concomitant medications that will be taken during the study, including all over-the-counter medications, vitamins, and nutritional supplements, will be recorded and should include at a minimum: start date, stop date or continuing, and indication/reason.

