7.3 Analysis Eligible Subjects

When considering subjects for inclusion in the re-infection analyses, it becomes apparent that some are not appropriate for consideration. As an example, if a subject is treated with an antibiotic for an illness and this antibiotic also treats GC and/or CT, then it is not possible to get a true reflection as to the re-infection prevention abilities of the product under investigation. Likewise, if a subject is found to be infected with GC and needs to be treated, the ability to later detect a CT infection is compromised. As such, for subjects to be eligible for CT (or GC) re-infection analyses, we require the following:

- 1) Known re-infection status through the end of the treatment phase (i.e., a determination of positive or negative re-infection can be definitively made per definitions below),
- 2) No use of prohibited antibiotic medications, and
- 3) No GC (or CT) re-infection, unless it is identified at the same time as the CT (or GC) re-infection.

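### SAP 7.3 drops women who took a listed CT/GC antibiotic whatever the reason, so some exclusions from the primary comparison are related to the outcome, and no planned efficacy analysis restores them

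*Protocol*

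**What the plan says.** The operative rule is in SAP 7.3. To enter the CT analysis a woman must have a known status through the end of treatment, must meet "No use of prohibited antibiotic medications", and must have no GC infection unless it is found together with CT. The antibiotic condition mentions neither indication nor timing. The only antibiotic example given for it is a drug taken for some other illness. SAP 8.8.1 takes this eligible subset of the mITT population as the primary denominator.

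Protocol 8.2 budgets for the rule: "5% will be deemed ineligible for analysis due to antibiotic use". Protocol 3.3 names nine drugs. Exclusion criterion 11 in Protocol 3.2, which has the same list, describes them as "specific antibiotics known to be used for the treatment of CT or GC".

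Under SAP 8.8.1 a CT event is a positive NAAT during Visits 1 to 5, and Protocol 5.6 sends NAAT specimens to a central laboratory. Neither document has a rule for a CT diagnosis made outside the study. Protocol 8.3.3 describes the analyzed women as those infected with CT or completing without re-infection, and does not name antibiotic use as a separate bar.

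Protocol 5.5.4 already collects the reason for each drug: concomitant medication records "should include at a minimum: start date, stop date or continuing, and indication/reason".

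**The concern.** The rule treats antibiotic use as a nuisance unrelated to the outcome. For these drugs in these women that is doubtful. Protocol 2 says they are at risk through untreated or new partners and permits standard-of-care treatment during the study. Scheduled swabs are four weeks apart. Protocol 5.9 leaves testing at unscheduled visits to the investigator, so no NAAT is required there. Needing a prohibited drug is a reason for withdrawal under Protocol 3.6.1.

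A woman can therefore be diagnosed at another clinic, or treated for symptoms or an infected partner, before a study swab records an infection. SAP 7.3 then removes her. The reason for removal is the outcome, or a marker of it, and it arises after randomization.

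At stake are the CT proportion in each arm, the difference between arms that the plan reports, and the power to detect it. If the chance of such treatment differs by arm, the comparison itself is also affected.

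**Working it through.** **Inputs from Protocol 8.2 (repeated in SAP 5).** CT risk 22.5% on placebo and 13% on AMPHORA; 253 analyzable women per arm; two-sided 5% level; losses of 20%, 15% and 5%; 844 enrolled, 422 per arm.

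**Reproducing the plan.** For the chi-square test with n per arm and mean risk p̄, power = Φ{(|p₁ − p₂| − 1.96·s₀)/s₁}, where s₀ = √[2p̄(1 − p̄)/n] and s₁ = √{[p₁(1 − p₁) + p₂(1 − p₂)]/n}.
- With 0.225, 0.13 and n = 253: p̄ = 0.1775, s₀ = 0.0340, s₁ = 0.0337. Power = Φ{(0.095 − 0.0666)/0.0337} = Φ(0.843) = 0.800, as stated.
- 506/(1 − 0.40) = 843.3, so 844, as stated. The 253 is thus already net of the 5% antibiotic loss.
- 5% of 844 is 42.2 women, about 21 per arm if split evenly.

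**Assumption.** The share of the 42 that is CT-related is not in the documents. Let f be the share of true CT cases treated and excluded before a study swab detects them, equal in both arms. The proportion left in the analysis is p′ = p(1 − f)/(1 − pf). Since 253 is already net of antibiotic exclusions, n stays at 253.

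For f = 10%:
- placebo: 0.225 × 0.9/(1 − 0.0225) = 0.2025/0.9775 = 0.2072
- AMPHORA: 0.13 × 0.9/(1 − 0.013) = 0.117/0.987 = 0.1185
- difference: 0.0886; power = Φ{(0.0886 − 0.0643)/0.0326} = 0.772

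Women removed per 422 are 422·p·f: 9.5 on placebo and 5.5 on AMPHORA. This is approximate, since it ignores other losses.

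| f | Placebo | AMPHORA | Difference (points) | Power | CT cases removed, placebo / AMPHORA | As share of the 42 |
|---|---|---|---|---|---|---|
| 0 | 22.5% | 13.0% | 9.5 | 80.0% | 0 / 0 | 0% |
| 5% | 21.6% | 12.4% | 9.2 | 78.7% | 4.7 / 2.7 | 18% |
| 10% | 20.7% | 11.9% | 8.9 | 77.2% | 9.5 / 5.5 | 36% |
| 20% | 18.8% | 10.7% | 8.2 | 73.7% | 19.0 / 11.0 | 71% |

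**Ratio measures.** The odds after removal are p′/(1 − p′) = (1 − f)·p/(1 − p). The factor (1 − f) cancels between arms, so the odds ratio stays at 0.515 for every f. The risk ratio goes from 0.578 to 0.567 at f = 20%.

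**Does another planned analysis cover this?** SAP 8.1 uses mITT for efficacy tables. The alternative definition in SAP 8.8.3 tightens only what counts as not re-infected. The adherence analyses subset women by product use. None brings back a woman excluded for antibiotics.

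**The case against.** The case against has real force on size.

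- *The assumed share may be high.* At f = 20%, about 30 of the 42 budgeted exclusions would be true CT cases. At f = 5% the loss is 0.3 points and little more than one point of power. Nothing in the documents fixes f. This stands.
- *The bias is conservative if f is equal by arm.* Blinding supports equal f. The absolute difference and power then fall, and the odds ratio does not move. A reader might infer a bias in favor of AMPHORA or an inflated type I error; under equal f there is neither.
- *Imbalance is not hidden.* A reader might suppose that the effect could not be seen in the planned output. SAP 8.3 tabulates reasons for exclusion from the CT and GC analyses by arm, and SAP 8.6 tabulates concomitant medications by arm. What is missing is a split by indication and an analysis that acts on it.
- *Outside diagnoses are a different kind of evidence.* Inclusion criterion 9 accepts outside evidence ("Lab reports confirming CT/GC infection OR" a clinic note), but to show past infection, not to adjudicate the endpoint. Using it in the primary analysis would change how events are ascertained. This stands, and it places such diagnoses in sensitivity analyses.
- *A treated woman may still test positive.* The documents do not say what her next swab would show, and Protocol 5.10 asks for a NAAT at early termination unless she was withdrawn for a positive one. That does not rescue her, because the antibiotic condition excludes her either way.

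Read literally, the SAP condition would also remove women treated after a positive study NAAT. Protocol 8.3.3 keeps women infected with CT, so this cannot be intended, and the point here does not rest on it. The text of SAP 7.2 on missing data was not available for this review and could bear on the matter.

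**Conclusion.** The point holds in a limited form. As written, SAP 7.3 makes an exclusion after randomization that is related to the outcome for any woman treated for CT or suspected CT before a study swab records it. No planned efficacy analysis reverses it.

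Its size is unknown. Over an assumed range of f from 5% to 20%, equal in both arms, the absolute difference is understated by 0.3 to 1.3 points and power falls by about 1 to 6 points, with the odds ratio unchanged. Under that assumption the bias is toward a smaller absolute effect.

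If treatment differs by arm, the direction is open. Appendix C tells women with burning or irritation to consult the site. If that led to more empirical treatment of uninfected women on AMPHORA, non-cases would leave that arm and its CT proportion would rise. If infected AMPHORA women were treated early more often than infected placebo women, the benefit would be overstated. The documents give no figure for either.

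**What to change.** In SAP 7.3 and Protocol 8.3.3, classify use of listed antibiotics during the intervention period, before any positive study NAAT, by recorded indication. Do this blind to treatment and before database lock, in three groups:

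1. laboratory-confirmed CT diagnosed outside the study;
2. treatment for suspected CT or partner exposure without a test;
3. treatment for an unrelated illness.

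Tabulate the groups by arm. Keep the primary event as a study NAAT. Add two pre-specified sensitivity analyses: one restores group 1 as CT infections, the other restores groups 1 and 2. Restored women enter both numerator and denominator in their randomized arm. Group 3 is handled as now. Do the same for GC.

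The cost is SAP and protocol wording, two extra tables per infection, and a blinded review of about 42 medication records if the planned 5% is right. No new data are needed, since the indication is already collected. Two limits should be stated with the results: outside tests are not central-laboratory results, and some women counted in group 2 will not have been infected.

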#### 8.3 Final Analysis Plan

#### **8.3.1** Analysis Populations

This study will utilize three analysis populations: Intention-to-Treat (ITT), modified Intention-to-Treat (mITT), and safety.

The ITT population will consist of all randomized subjects. The mITT population will consist of all randomized subjects who are negative for chlamydia and gonorrhea at enrollment and report

use of study product prior to at least one coital event. Lastly, the safety population will be based on subjects who applied any amount of study product.

Analyses using the ITT and mITT populations will be performed based on the treatment randomized. Meanwhile, safety analyses will be based on the treatment received.

#### 8.3.2 Randomization and Stratification

A randomized study group assignment schema, stratified by study site, will be developed using SAS, release 9.3 or higher.

#### 8.3.3 Procedures for Handling Missing, Unused, and Spurious Data

All analyses will be based on data as observed in the study. No imputations will be performed for data that are missing or spurious.

Given the need to provide treatment to subjects who become infected with CT and/or GC, not all subjects will be evaluable for each endpoint since the use of antibiotics would treat both possible infections. Therefore, the subjects analyzed for the primary efficacy endpoint are those that are infected with CT or who complete the study with no re-infections. Likewise, the subjects analyzed for the secondary efficacy endpoint are those that are infected with GC or who complete the study with no re-infections.

#### 8.3.4 General Statistical Considerations

All subjects that enter the study will be accounted for in the final clinical report, whether or not they are included in the analysis. All reasons for exclusion will be documented for those subjects.

For continuous variables, descriptive statistics will include the number of non-missing values, mean, standard deviation, median, minimum, and maximum. For categorical variables, descriptive statistics will include counts and percentages per category.

Baseline values for all parameters will be the most recent value prior to administration of study product or speculum exam.

#### 8.4 Planned Statistical Methodology

#### 8.4.1 Data Analysis for Efficacy

For the primary analysis, the proportion of subjects who experience at least one CT infection will be compared between the intervention groups (AMPHORA or placebo) using a Chi-square test.

The primary efficacy analysis will be completed using the subjects deemed analyzable (see Section 8.2) from the mITT population.

The primary statistical hypothesis being tested is that there is no difference in the proportion of subjects with CT infections in the AMPHORA intervention group versus placebo. In statistical terms:

$$H0: pAMPHORA = pplacebo, HA: pAMPHORA \neq pplacebo$$

where pAMPHORA and pplacebo denote the proportion of subjects with CT infections during the study while on AMPHORA or placebo, respectively. Denominators for percentages are number of subjects in the mITT population in each intervention group. To test superiority over placebo, the incident infection of CT will be compared against placebo based on a Chi-square test. The estimated difference in proportions, 95% confidence interval, and p-value will be presented. A two-sided 5% type I error rate ( $\alpha$ =0.05) will be used.

Similar analyses will be performed for incident infection of GC.

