## 2.1.2 Secondary Outcome Measures

The secondary outcome will measure the proportion of subjects who experience at least one urogenital GC infection during the study intervention period (incident infection of GC).

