8 STATISTICAL METHODS

8.1 General statistical conventions

All statistical procedures will be completed using SAS version 9.4 or higher on the SAS Grid.

Unless otherwise stated, all statistical testing will be two-sided and will be performed using a significance (alpha) level of 0.05. Two-sided 95% confidence intervals (CI) will be provided when relevant.

For continuous variables, descriptive statistics will include the number of non-missing values, mean, standard deviation, median, minimum, and maximum. For categorical variables, descriptive statistics will include counts and percentages per category. All summaries will be presented by treatment group, unless otherwise specified.

Baseline values for all parameters will be the most recent value prior to administration of study product or speculum exam.

All subject data will be presented in individual subject data listings. Unless otherwise stated, unscheduled visit results will be included in date/time chronological order, within patient listings only. All listings will be sorted by investigational site, patient number, and visit. The treatment group (AMPHORA, Placebo) as well as patient's age and sex (if available) will be stated on each listing. With respect to study tables, the mITT population will be used for efficacy analyses; safety population will be used for safety analyses.

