8.8.2 Analysis of secondary efficacy endpoint

Similar to the primary endpoint analysis, the incidence of urogenital GC infection will be described

using frequencies and percentages with the difference between treatment groups analysed using a Chi-Square test. Note: for a subject to be considered re-infected with GC any positive NAAT test during the treatment phase (visits 1-5) will constitute re-infection utilized. For a subject to be considered not re-infected, a subject with a negative NAAT at visits 1 & 5 with no positive NAATs in between is deemed not re-infected.

As a complementary analysis, tables will be created which also summarize re-infection by each scheduled visit.

GC infection information will be listed.

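### The secondary GC test runs at two-sided 0.05 whatever the CT result, so a GC finding could be reported as significant after CT has failed

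*Protocol*

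**What the plan says.** **CT.** Protocol 8.4.1 and SAP 8.8.1 give CT infection a written null and alternative hypothesis and a chi-square test. The level in Protocol 8.4.1 is "A two-sided 5% type I error rate".

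**GC.** Protocol 2.1.2 makes GC the secondary endpoint: "The secondary outcome will measure the proportion of subjects who experience at least one urogenital GC infection during the study intervention period". Its analysis in Protocol 8.4.1 is one sentence, "Similar analyses will be performed for incident infection of GC". SAP 8.8.2 begins "Similar to the primary endpoint analysis, the incidence of urogenital GC infection will be described" and continues "using frequencies and percentages with the difference between treatment groups analysed using a Chi-Square test". Neither sentence gives an alpha. That comes from SAP 8.1: "Unless otherwise stated, all statistical testing will be two-sided and will be performed using a significance (alpha) level of 0.05". Nothing in SAP 8.8.2 states otherwise.

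**Who is analysed.** Protocol 8.3.3 limits the CT analysis to women infected with CT or finishing without any re-infection. For GC it says "Likewise, the subjects analyzed for the secondary efficacy endpoint are those that are infected with GC or who complete the study with no re-infections". SAP 7.3 keeps a woman in both analyses when the two infections are found at the same time.

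**What is not stated.** The available text has no testing order, gatekeeping rule, alpha split or multiplicity adjustment, and does not say that the GC p-value is descriptive. The changes listed in SAP 9 add none. SAP 8.10 plans no interim analysis, so no alpha is spent elsewhere.

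**The concern.** The trial is labelled Phase 2B/3, and its CT and GC objectives are worded in parallel. Suppose CT gives p = 0.20 and GC gives p = 0.03. Under the plan, GC is significant at its applicable level, and no sentence says how to read that result beside a failed primary.

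This could occur in practice. The sample-size section assumes that 15% of enrolled women will be re-infected with GC. That is 0.15 × 844 = 126.6, or about 127 women, so the GC comparison would have a substantial number of events.

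At stake is the meaning of a GC finding. If the order of testing is settled only after the results are known, it cannot protect the error rate over the two endpoints.

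**Working it through.** **Inputs**
- CT: two-sided 0.05 (Protocol 8.4.1, SAP 8.8.1). GC: two-sided 0.05 (default in SAP 8.1).
- CT rates 22.5% and 13%; 253 analyzable per arm; about 80% power; losses of 20%, 15% and 5%; 844 enrolled, 422 per arm (Protocol 8.2 and 3.4, SAP 5).
- Assumptions, not in the documents: the joint CT and GC infection rates in step 3.

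**1. The plan's own figures.** The mean rate is (0.225 + 0.13)/2 = 0.1775.

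n per arm = [1.960 × √(2 × 0.1775 × 0.8225) + 0.842 × √(0.225 × 0.775 + 0.13 × 0.87)]² / 0.095² = (1.0591 + 0.4512)² / 0.009025 = 252.8, so 253.

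Power at 253 per arm is 80.04%. Enrolment is 506/(1 − 0.40) = 843.3, so 844. All three figures reproduce. They concern CT only; the documents give no GC power and no error rate over the two endpoints.

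**2. Any rejection, both nulls true.** Under independence: 1 − (1 − 0.05)² = 0.0975. Upper bound under any dependence: 0.05 + 0.05 = 0.10.

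**3. Allowing for shared women.** Women with no re-infection are the non-events in both tests, so the tests are positively correlated. Both chi-square tests were simulated 400,000 times per row with equal rates in the two arms. Each arm had 316 observed women (422 × 0.75, after the 20% and 5% losses).

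| CT only | GC only | Both | Correlation | Any rejection | False benefit |
|---|---|---|---|---|---|
| 19% | 15% | 0% | 0.20 | 9.68% | 4.86% |
| 16% | 15% | 0% | 0.18 | 9.69% | 4.88% |
| 13.5% | 15% | 0% | 0.17 | 9.65% | 4.83% |
| 16% | 5% | 0% | 0.10 | 9.63% | 4.83% |
| 14% | 13% | 2% | 0.28 | 9.58% | 4.81% |
| 12% | 11% | 4% | 0.39 | 9.49% | 4.77% |
| 8% | 7% | 8% | 0.60 | 8.71% | 4.33% |

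The simulation standard error for any rejection is about √(0.097 × 0.903/400,000) = 0.0005, or 0.05 percentage points. Small differences between rows should not be over-read. The range is about 8.7% to 9.7%.

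**4. Benefit direction only.** A two-sided 0.05 test has a 0.025 chance of a false result favouring AMPHORA. Over two independent tests this is 1 − 0.975² = 0.0494, against 0.025 for CT alone.

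**5. With a fixed sequence.** If the CT null is true, any false rejection requires CT to reject first, so the chance is at most 5%. If the CT null is false and the GC null is true, the only possible false rejection is on GC, again at most 5%. The rate over both endpoints is at most 5% in every case. CT is tested exactly as before, so step 1 is unchanged.

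**The case against.** The strongest reply is that the documents already rank the endpoints. The title names only CT. Protocol 8.1 states one hypothesis, about CT. Formal hypotheses and the sample size are given for CT alone, and GC infection enters the sample size only as a reason for ineligibility. A careful reader would treat GC as supportive. This stands as far as it goes: the ranking is real, but no sentence turns it into a rule for the GC test.

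Four stronger readings are tempting, and the documents do not support them:
- **That the primary conclusion is inflated.** It is not. There is one primary test and no interim look, so the CT error stays at 5%.
- **That 9.75% is the chance of a false efficacy finding.** It counts rejections in both directions and assumes independence, which the shared analysis sets contradict. The false-benefit figure is about 4.9%.
- **That GC has no error control, or that the plan authorises a GC claim after CT fails.** GC has its own 5% level, and no passage defines a GC success criterion. The gap is that nothing governs the two tests together.
- **That the plan runs 24 tests at 0.05.** That total, 2 × (1 + 5 × 2 + 1), adds the adherence-subset and alternative-definition repeats in SAP 8.8.3. Those 22 analyses are already classed as exploratory or sensitivity analyses, so the count should not be used as a measure of error.

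One limit remains. The text of SAP 7.2 was not available for this check. Its title concerns missing data and outliers, so a multiplicity rule there is unlikely, but this could not be confirmed.

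**Conclusion.** The point holds as a gap in the rules for the secondary endpoint. GC is tested at two-sided 0.05 unconditionally, so it could be reported as significant after CT fails.

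With both nulls true, the rate of any rejection over the two endpoints is about twice the 5% attached to each. The range of 8.7% to 9.7% rests on assumed infection and co-infection rates; the 10% bound does not. The false-benefit rate similarly rises from 2.5% to about 4.9% under independence, or 4.3% to 4.9% in the simulated range.

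This is a worthwhile, inexpensive improvement. It is not a defect in the primary analysis.

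**What to change.** Change the SAP only, before unblinding. In SAP 8.8.2, state that:
- CT is tested first at two-sided 0.05;
- GC is tested confirmatorily at two-sided 0.05 only if CT is significant;
- otherwise the GC p-value is reported as nominal.

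Add a matching entry in SAP 9. Protocol Section 8 leaves the full specification of methods to the SAP, so a protocol amendment is not needed for this.

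The cost is a few sentences. CT alpha, 80% power and N = 844 do not change. The small downside is that a confirmatory GC claim requires CT to succeed, which follows the ranking that the primary and secondary labels already imply.
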